6.0 TREATMENT PLAN

6.1. Overall descriptive narrative

At the first visit (Visit #1) (Day 1), informed consent will be obtained before starting any study procedures. AK lesions will be counted by [name] and his personally-supervised CCLCM medical student researcher using clinical criteria that include presence of a visible lesion with erythema (pink or red), presence of scale, and a gritty consistency by feel (palpation). Each identified lesion will be marked with a black pen. All the marked lesions will then be counted. As a back-up, the patient's face will be photographed with all the pen-marks in place, for later independent confirmation of lesions counts.

Photographs will be taken two ways. First, documentation of the pen-marked lesions on the face will be taken using CCF i-Phones that are routinely used in our clinic; these digital photographs will be transferred and stored directly in each study patient's electronic (Epic) record.

Second, for photographic documentation of inflammation, the patient will also be photographed by a professional photographer using standardized lighting and multiple views to document the degree of inflammation at baseline.

The skin will be degreased with an alcohol wipe, lesions gently abraded with fine sandpaper, and a thin layer of ALA gel (Ameluz®) will be applied to the entire face. No occlusive dressing will be used. For patients in group **A**, the ALA gel will be left on for 10 min, and then positioned in front of the red light and exposed for 20 min; this is a (10 + 20) regimen. Patients in group **B** and group **C** will receive a (20 + 10) regimen or (60 + 10) regimen, respectively.

Pain will be assessed by asking the patient to rate their perceived pain level on an 11-point VAS scale (0= no pain, 10 = intolerable pain). Patients will be asked to report their VAS score at 1 minute after red light begins, and at the 5 minute mark (when the RhodoLED beeps). They will be asked for a final VAS score immediately after the light is turned off.

To assess side effects, patients will receive a 6-day questionnaire to record their side-effects daily during the coming week, and which asks them to confirm that they completely avoided any sun exposure during the first two days after PDT. Patients will also receive a standard set of instructions for home aftercare that includes Aquaphor emollient, a topical steroid if necessary for comfort, and instructions to wear sunscreen and avoid sunlight for 48 hr.

At the **second visit (Visit #2)** (Day 3 ± 1 day), the patient will be photographed by our professional photographer using standardized lighting and multiple views, to document the degree of inflammation at 3 days after red light PDT.

At the **third visit (Visit #3)** (Week 8 ± 1 week), lesions will again be marked and counted. Photographs will be taken using CCF iPhones that are routinely used to document the marked lesions on the face. These digital photographs will be transferred and stored directly in each study patient's electronic (Epic) record.

If any remaining lesions are identified, the skin will be degreased with an alcohol wipe, lesions gently abraded with fine sandpaper, and a thin layer of ALA gel (Ameluz®) will be applied to the entire face. No occlusive dressing will be used. For patients in group **A**, the ALA gel will be left on for 10 min, and then positioned in front of the red light and exposed for 20 min; this is a (10 + 20) regimen. Patients in group **B** and group **C** will receive a (20 + 10) regimen or (60 + 10) regimen, respectively.

Pain will be assessed by asking the patient to rate their perceived pain level on an 11-point VAS scale (0= no pain, 10 = intolerable pain). Patients will be asked to report their VAS score at 1 minute after red light begins, and at the 5 minute mark (when the RhodoLED beeps). They will be asked for a final VAS score immediately after the light is turned off.

To assess side effects, patients will receive a 6-day questionnaire to record their side-effects daily during the coming week. They will also receive a standard set of instructions for home aftercare that includes Aquaphor emollient, a topical steroid if necessary for comfort, and instructions to wear sunscreen and avoid sunlight for 48 hr.

The **fourth (final) visit (Visit #4)** will occur at 3-6 months after Visit 1, for final lesion counts, photographs using department iPhone, and administration of a patient satisfaction questionnaire.

(See section 11.0 for more details about the Visit Calendar)

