11.0 STUDY PARAMETERS AND DETAILED STUDY CALENDAR

Details of 10% ALA application and red light treatment were described in detail under Section 6.0, “Treatment Plan”. The timing of visits is summarized below and in section 11.5 (“Calendar”).

11.1 **PDT treatment (Visit 1)**

All AK lesions are measured clinically and photographed. The clinician applies 10% ALA gel to entire face, without occlusion, and allows it to incubate if for either 10 min, 20 min, or 60 min, depending upon the study arm assignment. The patient will then be exposed to red light (BF-RhodoLED® device) for either 10 min or 20 min, as per the assigned study arm.

11.2 **Post-treatment assessment of side-effects (Visit 2)**

The patient will return at day 3 (± 1 day) for facial photographs to document their erythema reaction. They will also be asked about their side-effects, and insure that they know to fill out the side-effects questionnaire during the 6 days post-PDT.

11.3 **PDT treatment (Visit 3)**

This will occur 8 weeks (± 1 week) after Visit 1. All AK lesions will be measured clinically and photographed and if any remain, then the same PDT treatment regimen used at Visit 1 will be employed again here for a second round of treatment.

11.4 **Final observation (Visit 4)**

This will occur 3-6 months after Visit 1. The subject will return for final skin exam, lesion counts, and photography. A patient satisfaction questionnaire will also be administered at this visit. The large scheduling visit window is designed to maximize the likelihood of patient compliance, since many patients with AK are retirees who spend many months traveling and spend their winters in warmer climates far from Cleveland.

11.5 **Study Calendar**

CALENDAR. Timeline of procedures for patients enrolled in the study.

	VISIT 1 PDT treatment session #1	VISIT 2 Photos of skin redness	VISIT 3 PDT treatment session #2	VISIT 4 Final lesion counts
Scheduled visit: → Procedure: ↓	Day 1	Day 3 ± 1 day	Week 8 ± 1 week	Month 3-6
Sign informed consent	X			
Examine patient, mark each lesion with a pen, and count the lesions	X		X	X
Take photographs in our professional studio (frontal view and side views) to document inflammation.	X	X		
Take photographs using clinic iPhone camera to document lesion counts (pen-marks)	X		X	X

Apply topical ALA gel and incubate for 10, 20, or 60 min prior to turning on the light source (as per assigned study arms A, B, or C, respectively)	X		X	

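### No masking of the lesion counters is planned, and the photographs meant for independent confirmation already show the first counter's pen marks

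*Combined protocol and SAP*

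**What the plan says.** Section 6.1 has lesions counted at Visit 1 by the investigator and a "personally-supervised CCLCM medical student researcher using clinical criteria that include presence of a visible lesion", together with scale and a gritty feel on palpation. Each lesion is marked in pen and the marks are counted. As a back-up, the face is "photographed with all the pen-marks in place, for later independent confirmation of lesions counts".

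At Visit 3, "lesions will again be marked and counted", and on the images: "Photographs will be taken using CCF iPhones that are routinely used to document the marked lesions on the face". Visit 4 is "for final lesion counts, photographs using department iPhone". The calendar in 11.5 covers the count photographs at Visits 1, 3 and 4 in a single row, which describes them as documenting the pen marks. Studio photographs are taken at Visits 1 and 2 only. Those at Visit 1 serve "to document the degree of inflammation at baseline", not counting.

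Under 5.2 a patient is enrolled on signing consent, and under 5.3 the arm is assigned on enrollment, from a scheme generated by the Research Pharmacy. No section describes masking of the counters. Section 12.0 makes the counts after two treatments the final efficacy outcome and the basis of the non-inferiority analysis.

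**The concern.** Deciding whether a spot is an actinic keratosis is a clinical judgement, and it is made by the team that ran the treatment. Section 1.3 states in advance that equivalent clearance is expected. Nothing keeps the arm from the counters, and the regimens differ visibly in timing.

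The planned check does not restore independence. A reader of a marked photograph is told, spot by spot, what the first counter decided. Agreement with those marks is weak evidence that the count was right. At Visits 3 and 4, which supply the numerator of clearance, there is no planned image without marks to return to.

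If knowledge of the arm shifted the counts even modestly, the difference between arms would move with it, and the stored material would not show it.

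**Working it through.** **1. Order of events.** Consent is signed (5.2), assignment follows on enrollment (5.3), and all Visit 1 procedures come after consent (6.1). The arm can therefore be known when the baseline lesions are marked.

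**2. Images available for a later check (6.1, 11.5).**

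| Visit | Count photograph | Other image | Unmarked image planned for counting |
|---|---|---|---|
| 1 | Phone, marks in place | Studio, for inflammation; order relative to marking not stated | No |
| 2 | None (no count) | Studio, for inflammation | Not applicable |
| 3 | Phone, marked lesions | None | No |
| 4 | Phone, pen marks per calendar | None | No |

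**3. The plan's own figure (14.2).** Inputs: 10 per group, margin 25, true difference 10, SD 13, two-sided alpha 0.05, 80% power.

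- SE of the difference = 13 × √(2/10) = 5.81; (25 − 10)/5.81 = 2.58.
- One-sided 0.05: Φ(2.58 − 1.645) = 82.5%; exact t with 18 df, 79.9%.
- One-sided 0.025: Φ(2.58 − 1.960) = 73.2%; exact t, 68.5%; the formula then asks for 12 per group.

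The stated 80% is reproduced at one-sided 0.05. The sidedness of alpha is a separate matter, so both levels are carried below.

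**4. One lesion in one patient.** Change in clearance = 1 / baseline count. Only the minimum of 10 is in the documents (4.1); 20 and 30 are assumed.

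| Baseline lesions | Change in clearance | Share of 25-point margin |
|---|---|---|
| 10 (minimum) | 10 points | 40% |
| 20 (assumed) | 5 points | 20% |
| 30 (assumed) | 3.3 points | 13% |

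At 10 lesions, one call separates 10/10 from 9/10 (100% clearance) and 8/10 from 7/10 (75% clearance). Both thresholds are listed in 12.0. The baseline count matters too: one doubtful spot marked at baseline and later called clear turns 7/10 = 70% into 8/11 = 72.7%.

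**5. From patient to arm.** The margin is taken here as a difference in mean clearance, as in 14.2. With 10 patients, one lesion in one 10-lesion patient moves the arm mean by 10/10 = 1 point. A 5-point shift needs one lesion in half the patients at 10 lesions each, or in every patient at 20. A 10-point shift needs one lesion in every patient at 10.

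**6. Illustration of what is at stake.** Let the true deficit equal the margin, and let counting bias favour the short regimen by b points. The chance of falsely declaring non-inferiority is P(T > critical t), where T is noncentral t with 18 df and noncentrality b/5.81. The values of b are assumed.

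| b (points) | One-sided 0.05 | One-sided 0.025 |
|---|---|---|
| 0 | 5.0% | 2.5% |
| 2.5 | 10.9% | 6.0% |
| 5 | 20.7% | 12.6% |
| 10 | 50.4% | 37.0% |

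This is a two-arm comparison within the study with SD 13. A larger SD would make the same bias inflate the error less.

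**The case against.** Several points on the other side have force.

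- **The marks may not hide the lesions.** A reader might infer that the photographs permit nothing but a recount of marks. The protocol says lesions are marked, not covered. A mark beside or around a lesion leaves it visible, and a missed lesion would carry no mark at all. So a marked photograph steers its reader but is not useless. It still does not allow an independent judgement.
- **Masking does not reach the main stated comparison.** Section 14.1 compares each regimen with the standard one, and 14.2 takes that standard from published 3-hour data. Every study patient is known to have had a short regimen, so hiding A, B or C leaves observer bias in that comparison. However, 1.3 calls regimen C the control, and the sample-size sentence compares each intervention with a control group, so contrasts among the arms still carry weight.
- **No error rate is documented.** A reader might infer from the tables that counts will be biased by a lesion per patient, or that the counters are shown to know the arm. Neither is in the documents. They are silent on masking, and the bias values are assumptions.
- **The student's count could be less reliable.** The student works under the investigator's personal supervision. A reader might infer that a masked student count should replace the investigator's as primary. That exchanges possible bias for possible loss of diagnostic accuracy, and the documents give no basis for preferring it.
- **This is a 30-patient pilot** (1.2) seeking suggestive evidence (1.3). That limits how much machinery is reasonable, but not the case for a nearly free safeguard.

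**Conclusion.** The point holds in this form: no masking of the counters is planned, assignment can be known before the baseline count, and the confirmation photographs carry the first counter's marks, with no unmarked image planned at Visit 3 or 4. The primary efficacy count therefore has no independent check.

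The exposure is 10 points of one patient's clearance per lesion at the 10-lesion minimum, and less at higher counts. At arm level, an assumed 5-point bias would raise the false non-inferiority rate from 5.0% to 20.7% (one-sided 0.05) or from 2.5% to 12.6% (one-sided 0.025). Whether any bias would occur, and how large it would be, cannot be learned from the documents. No design figure changes. The matter is worth correcting because the remedy is cheap, not because the counts are shown to be wrong.

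**What to change.** Amend 6.1 and the calendar in 11.5.

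1. At Visits 1, 3 and 4, take one unmarked phone photograph before pen-marking. Store a copy under study ID without the arm, apart from the Epic chart where count photographs now go and where study notes are also entered. Use the unmarked images for the confirmation already planned.
2. Have the Research Pharmacy release the assignment only after the baseline count is recorded.
3. Where feasible, keep the student already named out of treatment and unaware of the arm. The student records a separate count before the investigator does, at Visit 3 (before treatment) and Visit 4. Report it as a sensitivity check on the investigator's count. Write its independence into the text, because the student is supervised by the investigator. Ask patients not to mention their regimen.

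The cost is about a minute per visit plus simple filing, with no added visits. Step 3 depends on the student's availability, which the documents do not describe.

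Some limits remain. Photographs cannot capture palpation, which only the separate live count addresses. Patients may still reveal their regimen. Masking helps the comparisons among A, B and C only. None of this alters any treatment rule.

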6.2 Duration of Therapy

Each PDT therapy session (Visit 1 and Visit 3) will last for no more than 2 hours, depending upon which arm of the study the patient is in.

6.3 Duration of Follow Up

Patients will be followed until the end of Visit 4, which must occur within a follow-up window of 3-6 months after Visit 1. Thus the maximum duration of F/U is 6 months.

7.0 DOSING DELAYS / DOSE MODIFICATIONS: n/a

8.0 ADVERSE EVENTS: LIST AND REPORTING REQUIREMENTS

The following is a list of AEs and the reporting requirements associated with observed AEs.

The clinical course of each event will be followed until resolution, stabilization, or until it has been determined that the study treatment or participation is not the cause. Serious adverse events that are still ongoing at the end of the study period will necessitate follow-up to determine the final outcome. Any serious adverse event that occurs after the study period and is considered to be possibly related to the study treatment or study participation will be recorded and reported immediately.

8.1 Adverse Events and Potential Risks

8.1.1 *Ameluz®*

Aminolevulinic acid (ALA) is a natural component found in all cells in the human body. Ameluz is 10% ALA suspended in a lipid-based nanoemulsion. The application of ALA is not associated with any risks or side effects.

8.1.2 *Photodynamic Therapy*

When ALA is converted into PpIX in tumor cells, and illuminated with light, the following signs and symptoms are known to occur as part of the therapeutic response:

- (i) Stinging and/or burning sensation: >50%
- (ii) Erythema (localized redness): 35%
- (iii) Edema, localized: >35%
- (iv) Peeling, transient: <50%
- (v) Blister formation: rare

8.1.3 *Photodynamic Therapy response (with local cutaneous effects):*

The constellation of transient local symptoms of stinging and/or burning, itching, erythema and edema as a result of topical application of ALA followed by illumination with red light has been observed in clinical studies; for example see ref [14]. Stinging and/or burning subsides between 1 min and 24 hours after the light is turned off, and appears qualitatively similar to that perceived by

patients with erythropoietic protoporphyrin upon exposure to sunlight. There is no clear drug dose or light dose dependent change in the incidence or severity of stinging and/or burning.

8.1.4 *Extra-cutaneous adverse experiences reported:*

In previous studies, no non-cutaneous adverse events were found to be consistently associated with Ameluz application followed by red light exposure. No clinically significant patterns of clinical laboratory changes were observed for standard serum chemical or hematologic parameters in any of the controlled clinical trials.

8.1.5 *Safety in pregnancy:*

No carcinogenicity testing has been carried out using ALA. No evidence of mutagenic effects was seen in four studies conducted with ALA to evaluate this potential. No assessment of effects of ALA on fertility has been performed in laboratory animals. It is unknown what effects systemic exposure to ALA might have on fertility or reproductive function. Therefore, Ameluz is considered as Pregnancy Category C.

8.2 Definitions

8.2.1 *Adverse Events*

An **adverse event** (AE) is any unfavorable or unintended event, physical or psychological, associated with a research study, which causes harm or injury to a research participant as a result of the participant's involvement in a research study. The event can include abnormal laboratory findings, symptoms, or disease associated with the research study. The event does not necessarily have to have a causal relationship with the research, any risk associated with the research, the research intervention, or the research assessments.

Adverse events may be the result of: (a) the interventions and interactions used in the research; (b) the collection of identifiable private information in the research; (c) an underlying disease, disorder, or condition of the subject; and/or (d) other circumstances unrelated to the research or any underlying disease, disorder, or condition of the subject. In general, adverse events that are at least partially the result of (a) or (b) would be considered related to the research, whereas adverse events solely related to (c) or (d) would be considered unrelated to the research.

External adverse events are adverse events experienced by subjects enrolled in multicenter clinical trials at sites other than the site(s) over which the Institutional Review Board has jurisdiction.

Internal adverse events are adverse events experienced by subjects enrolled at the site(s) under the IRB's jurisdiction for either multicenter or single-center research projects.

8.2.2 The significance of an adverse event is used to describe the patient/event outcome or action criteria associated with events that pose a threat to a patient's life or functioning (i.e., moderate, severe or life threatening). Based on the National Cancer Institute Guidelines for the Cancer Therapy Evaluation Program, severity can be defined by the following grades of events:

Grades 1 are mild adverse events. (e.g., minor event requiring no specific medical intervention; asymptomatic laboratory findings only; marginal clinical relevance)

Grades 2 are moderate adverse events (e.g., minimal intervention; local intervention; non-invasive intervention; transfusion; elective interventional radiological procedure; therapeutic endoscopy or operation).

Grades 3 are severe and undesirable adverse events (e.g., significant symptoms requiring hospitalization or invasive intervention; transfusion; elective interventional radiological procedure; therapeutic endoscopy or operation).

Grades 4 are life threatening or disabling adverse events (e.g., complicated by acute, life-threatening metabolic or cardiovascular complications such as circulatory failure, hemorrhage, sepsis; life-threatening physiologic consequences; need for intensive care or emergent invasive procedure; emergent interventional radiological procedure, therapeutic endoscopy or operation).

Grades 5 are fatal adverse events resulting in death.

8.2.3 Serious Adverse Events

A *serious adverse event* (SAE) is any adverse experience occurring at any dose that results in any of the following outcomes:

- Results in *death*.
- Is a *life-threatening* adverse experience. The term life-threatening in the definition of serious refers to an adverse event in which the subject was at risk of death at the time of the event. It does not refer to an adverse event which hypothetically might have caused death if it were more severe.
- Requires *inpatient hospitalization or prolongation of existing hospitalization*. Any adverse event leading to hospitalization or prolongation of hospitalization will be considered as Serious, UNLESS at least one of the following expectations is met:
 - The admission results in a hospital stay of less than 12 hours OR
 - The admission is pre-planned (i.e., elective or scheduled surgery arranged prior to the start of the study) OR
 - The admission is not associated with an adverse event (e.g., social hospitalization for purposes of respite care).

However it should be noted that invasive treatment during any hospitalization may fulfill the criteria of “medically important” and as such may be reportable as a serious adverse event dependant on clinical judgment. In addition where local regulatory authorities specifically require a more stringent definition, the local regulation takes precedent.

- Results in *persistent or significant disability/incapacity*. The definition of disability is a substantial disruption of a person’s ability to conduct normal life’s functions.
- Is a *congenital anomaly/birth defect*.
- Is an *important medical event*. Important medical events that may not result death, be life-threatening, or require hospitalization may be considered a serious adverse experience when, based upon appropriate medical judgment, they may jeopardize the patient or subject and may require medical or surgical intervention to prevent one of the outcomes listed in this definition. Examples of such medical events include allergic bronchospasm requiring intensive treatment in an emergency room or at home, blood disease or disorders, or

convulsions that do not result in inpatient hospitalization, or the development of drug dependency or drug abuse.

